7.1.6 Efficacy Evaluation Method

1) Description of efficacy parameters

The primary efficacy endpoint is defined as the proportion of subjects achieving Grade A healing (success) of surgical incision in each group.

According to clinical routine practice, wound healing status should be assessed during removal of stitches of incision and generally, stitches at the incision of head, face and neck are taken out on Day 4-5 post-surgery; however, if energy devices are used (e.g. electrotome), the removal of stitches should be delayed by 1-2 days. In this study, all the skin layers can be performed with intradermal continuous suture using absorbable sutures, thus it is unnecessary to take out stitches at the incision. Therefore, the time of wound healing assessment in this study is set as Day 5-7 post-surgery.

Wound healing status is classified into three grades:

- Grade A healing: Good healing with no adverse reaction;
- Grade B healing: Inflammatory reaction(s) at the healing, such as red swelling, induration, hematoma, effusion, etc., but without suppuration;
- Grade C healing: Suppuration of incision, requiring incision and drainage and other treatments.

Secondary Efficacy Endpoints include:

1. Incision suturing time, defined as the time required from the first needle insertion for stitching ribbon muscles to the completion of intradermal suture (min);
2. Modified Hollander Wound Evaluation Scale (see Annex 3), assessed by Imaging Center evaluators using pictures, including: a picture of complete neck anterior view containing full length of the incision, a picture taken parallel to the incision plane, a picture taken at a 45° angle to the incision plane, and incision lateral view pictures of both sides (one for each);
3. Postoperative incision pain score (VAS scale, see Annex 4-1);
4. Health related quality of life scale (EQ-5D-5L): Subjects are required to select the most appropriate levels in 5 aspects to determine their health status (see Annex 5):
 - Motility
 - Self care
 - Daily activities
 - Pain/discomfort
 - Anxiety/depression

2) Selection of method and time to evaluate, record and analyze the efficacy parameters

The primary efficacy endpoint (wound healing grade) will be assessed by independent, blinded Imaging Center according to the picture (a picture of complete neck anterior view, containing full length of the incision) on Day 5-7 post-surgery and documented in the e-CRF.

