- g. Assessed by Central Imaging evaluators using imaging data provided by study sites.
- h. Including incisional wound separation or wound dehiscence requiring intervention, target incisional wound healing delay, etc.

- i. For subjects who are randomized but without any of study sutures used for incision closure, this visit is conducted as early as possible. For subjects who withdraw ICF, this visit is conducted as early as possible with subjects' permission. Telephone visit is acceptable.

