Control group: Use the control device ██████████) for continuous suture of the ribbon muscles, ██████████) for interrupted suture of the platysma, and the control device ██████████) continuous subcuticular suture.

Control group			
Level	Suture Material	Suture Technique	Product Code
Ribbon muscles	██████████	Continuous	██████████
Platysma	██████████	Interrupted	██████████
Intradermal	██████████	Continuous	██████████

None study product should be used once incision closure, despite of any reason leading to original sutures removal, incisions re-opening or re-suturing.

The method of use of the investigational devices is as follows:

1. Secure the fixation loop portion to robust tissue by taking a bite in the designated tissue, passing the needle through the loop and pulling tautly around the anchoring tissue.
2. After the device is anchored into the tissue, grasp the strand and approximate tissue to the desired tension. Bites, or passes through the tissue, can be taken in a continuous suturing technique to approximate the wound. Care should be taken to utilize the device on the barbed segments only. Do not attempt to approximate wounds using the non-barbed segment near the needle, as the barbs are required for successful wound approximation with the device.
3. (1) To complete the closure in subcuticular closure, take at least one pass in the reverse direction. Then pass the needle across the incision and take a split thickness bite perpendicular to the incision and exit the skin.
(2) To complete the closure in all other tissue layers, take at least two passes in the reverse direction to complete the closure
4. Then gently pull on the free end of the device and cut flush with the surface of the tissue.
To remove the entire device: Cut the device at the end anchored with the loop, and then pull the distal end to remove the device.

Other sutures used in the trial should be used as per surgical procedure. Do not use skin adhesive at the incision site after the suture is done.

Postoperative care:

Postoperative care should be given according to the routine practice of the study site or the

specific requirements of postoperative care guidelines. The subjects' condition should be closely monitored until they are discharged.

4) Visit 4 – Day 5-7 post-surgery

The following information must be obtained at this visit:

- Concomitant medications;
- Concomitant treatment;

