the two group comparisons, the p-value associated with the non-inferiority test will be calculated using the Normal approximation Z (pooled) statistic. If the smaller p-value is smaller than 0.0125, then the null hypothesis associated with this p-value will be rejected and it will be concluded that the associated Test product is non-inferior to Control; subsequently, the larger p-value will be compared to 0.025 in order to test the non-inferiority of the other Test product to Control. If the smaller p-value is larger than 0.0125, then neither of the null hypotheses can be rejected and it will be concluded that, for both investigational devices, the study failed to demonstrate non-inferiority to Control.

The primary endpoint will be analyzed using the Full Analysis Set (FAS) and Per-Protocol (PP) sets. The PP analysis will be considered the primary analysis, while the FAS analysis will be considered supportive. The analysis sets for this study are defined in section 8.8.

The following **secondary efficacy endpoints** will be summarized descriptively by treatment group for the FAS:

1. Incision suturing time, defined as the time required from the first needle insertion for stitching ribbon muscles to the completion of intradermal suture (min);
2. Modified Hollander Wound Evaluation Scale;
3. Postoperative incision pain score (VAS Scale);
4. Health related quality of life scale (EQ-5D-5L).

In addition, the following safety endpoints will be summarized descriptively t by treatment group for the Safety analysis set:

1. Incidence of postoperative SSI;
2. ASEPIS score (only assessed in subjects with confirmed SSI);
3. Incidence of incisional wound separation or wound dehiscence requiring intervention;
4. Incidence of delayed incisional wound healing events;
5. Incidence of other AEs;
6. Product complaints.

The incidence of AEs will be assessed according to the classification of event and summarized descriptively by treatment groups. Incidence of AEs will also be assessed by onset time (intraoperative or postoperative), relationship to study surgical procedure, relationship to the study product, severity, and seriousness.

All continuous variables will be summarized by number of subjects, mean, standard deviation, median, minimum and maximum. All categorical data will be summarized by frequencies and associated percentages. No inferential statistics will be generated for secondary efficacy and safety endpoints.

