8.8 Selection Criteria and Reason of Subjects Included in the Analysis

All subjects that meet the inclusion/exclusion criteria are considered to meet the requirements for recruitment.

Three analysis sets in the study are defined for this study, as follows:

- FAS consists of all the enrolled subjects who were randomized and for whom the randomized suture materials were used for incision closure.
- PP (evaluable) Set contains all the subjects in the FAS who have no major protocol

deviation, have data available for primary efficacy endpoint and do not meet any of the following criteria:

- Subject undergoes any of the following procedures, in addition to thyroidectomy:
 - 1、 Any surgical procedure which require additional neck incisions or extend the original incision;
 - 2、 Cervical lymph node dissection (except the dissection of lymph nodes in the VI area);
 - 3、 Other unplanned surgical procedures (except the procedure that the investigator doesn't think it will affect the original incision's healing)
- Subject's intraoperative frozen pathology or postoperative paraffin section pathology suggests anaplastic thyroid cancer;
- Subject receives any surgical procedures that lead to re-opening of the cervical incision during the period from the wound closure to the completion of study, except for surgeries related to surgical incision complication or study device.
- Safety Set contains all the enrolled subjects who receive surgery.

Major protocol deviations are deviations that have an impact on the primary endpoint assessment or randomization. These will be determined prior to database lock.

The analysis of primary efficacy endpoint will be performed using FAS and PP Sets. However, while the primary analysis is based on the PP Set, FAS analysis will only be used as supplemental analysis.

The secondary efficacy endpoints will be analyzed using the FAS, while the safety endpoints will be analyzed using the Safety Set.

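### No rule scores a study closure that fails and is redone before the Day 5-7 photo as a failure: it can be graded A, or drop out of the primary analysis

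*Protocol*

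**What the plan says.** **Analysis set.** Protocol 8.1 and SAP 13.1.2 make PP primary: "The PP analysis will be considered the primary analysis". Protocol 8.8 and SAP 5.2 exclude a subject whose cervical incision is re-opened at any time from closure to study completion, "except for surgeries related to surgical incision complication or study device". The same list also excludes subjects who have other unplanned surgical procedures, unless the investigator thinks healing of the original incision is unaffected. Subjects with major deviations are excluded as well, and Protocol 8.8 defines these broadly: "Major protocol deviations are deviations that have an impact on the primary endpoint assessment or randomization".

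**Re-closure.** Protocol 7.2.3 says: "None study product should be used once incision closure, despite of any reason leading to original sutures removal, incisions re-opening or re-suturing". The sentence is awkward, but both plausible readings mean that a re-closure uses non-study material. Such a re-closure is then not in itself a deviation.

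**Endpoint.** Protocol 7.1.6 takes the grade from one anterior-view Day 5-7 picture: it "will be assessed by independent, blinded Imaging Center according to the picture". The footnote to the schedule in 7.2.1 describes the graders' input: "Assessed by Central Imaging evaluators using imaging data provided by study sites". The top grade is defined as "Grade A healing: Good healing with no adverse reaction".

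**Denominator and missing data.** The success proportion counts everyone whose wound was closed with the randomized suture (Protocol 8.1, SAP 13.1.2). Nothing is imputed (Protocol 8.7, SAP 7.1). Separation or dehiscence needing intervention is a safety endpoint and is summarised only descriptively (Protocol 8.1, SAP 14).

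**The concern.** The trial is meant to show that barbs do no harm to efficacy or safety (Protocol 4.3). A study closure that had to be redone is an outcome that such a trial must count. As written, the subject is retained but the event does not enter the endpoint. The photograph may show a wound held by a suture that is not under study, read by graders to whom no text gives the clinical history.

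Removing the subject does not help, because the failure then vanishes from the primary analysis. Either route can take failures out of the count, which tends to favour a non-inferiority claim.

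The same PP criterion has a smaller timing fault. A re-opening unrelated to the incision or device removes the subject even if it happens after a valid Day 5-7 grade, up to Day 28-35. Such an event cannot have affected that grade.

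**Working it through.** **1. The planned size reproduces.** Inputs from Protocol 8.2.1 and SAP 13.1.1: success 0.98 in both arms, margin 0.05, one-sided 0.0125, power 80%.

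n = (2.2414 + 0.8416)² × 2 × 0.98 × 0.02 / 0.05² = 149.04, rounded up to 150 per arm. Then 150 / 0.90 = 166.7, rounded up to 167, and 3 × 167 = 501. All three figures agree with the plan. At 98% success, 150 × 0.02 = 3 failures per arm are expected.

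**2. How many failures decide the result.** The planned statistic (Protocol 8.1, SAP 13.1.2) is

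Z = (p_T − p_C + 0.05) / √(p̄(1 − p̄) × 2/150), where p̄ is the pooled success proportion.

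With 3 control failures in 150:

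| Test failures | p̄ | Numerator | Z | One-sided p | First step (0.0125) | Second step (0.025) |
|---|---|---|---|---|---|---|
| 4 | 293/300 | 0.0433 | 2.486 | 0.0065 | pass | pass |
| 5 | 292/300 | 0.0367 | 1.971 | 0.0244 | fail | pass |
| 6 | 291/300 | 0.0300 | 1.523 | 0.0639 | fail | fail |

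One re-closed wound graded A turns 5 failures into 4, which changes the first Holm step. If the other suture has already passed, 5 failures are enough at the second step, and the change then matters between 5 and 6.

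**3. Effect on the error rate at the margin.** True failure rates are 7% (test) and 2% (control), with 150 per arm. The chance of declaring non-inferiority at 0.0125 is found by summing exact binomial probabilities over all outcomes that pass the planned test. The documents give no re-opening rate, so every hidden amount below is an assumption.

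| Assumed hidden failures | Apparent failure rates, test / control | Hidden subjects per 150, test / control | P(declare non-inferiority) |
|---|---|---|---|
| None | 7.00% / 2.00% | 0 / 0 | 2.3% |
| 5% of failures in each arm | 6.65% / 1.90% | 0.5 / 0.2 | 3.0% |
| 10% of failures in each arm | 6.30% / 1.80% | 1.1 / 0.3 | 4.0% |
| 20% of failures in each arm | 5.60% / 1.60% | 2.1 / 0.6 | 6.8% |
| Equal 0.5 point in each arm | 6.50% / 1.50% | 0.75 / 0.75 | 2.7% |
| Equal 1 point in each arm | 6.00% / 1.00% | 1.5 / 1.5 | 3.4% |

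The 2.3% in the first row, against a nominal 1.25%, belongs to the pooled Z and not to this issue. Only the rise above it is relevant here. A proportional share hides 7/2 = 3.5 times as many subjects in the test arm and shrinks the true 5-point deficit to 4.75, 4.5 or 4.0 points. Hiding equal points leaves the deficit at 5, and the rise is smaller.

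**4. Routes by which the failure can be lost.** (a) The re-closed wound looks good on the photo and is graded A. (b) There is no photo, so the PP requirement for primary-endpoint data is not met and nothing is imputed. (c) The unplanned-procedure criterion or the deviation review removes the subject. No text in either document closes any of these routes.

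**The case against.** - **Retention in PP is not certain.** The unplanned-procedure and major-deviation criteria could remove such a subject, and set membership is agreed before unblinding (SAP 5). This stands: the documents are ambiguous between keeping and excluding. Exclusion loses the failure too, so the gap remains, but the fix must cover both routes.
- **A reader might infer that the worst closure failures become successes.** The documents do not support that. Grade A requires freedom from adverse reaction, and swelling, induration, hematoma or effusion is Grade B (Protocol 7.1.6). Some re-closed wounds will be graded B or C. They can become successes; nothing shows that they will.
- **A reader might assume that a large share is hidden.** A 40% share would give 19%, but no re-opening rate is given, and a Grade B failure needs no re-opening. Smaller assumptions give 2.7% to 4.0%.
- **Any binary endpoint has a boundary subject.** True. Step 2 shows sensitivity, not bias.
- **The events are still reported.** Separation or dehiscence, delayed healing, infection and adverse events are tabulated by arm, so they are not concealed from a reader of the report. They simply do not enter the non-inferiority test.
- **The late-exclusion clause is minor.** Agreed. It covers only unrelated re-openings, no direction of bias is shown, and the FAS has no such exclusion.

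**Conclusion.** The gap is real and should be fixed, but its size is unknown. Followed as written, the plan can score a study closure that failed before the Day 5-7 photo as Grade A, or lose it, and no rule counts it as a failure. A re-opening after the photo cannot change the grade already given.

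One such subject can change the first Holm step when control failures are at their expected 3. For a suture at the margin, the chance of a false claim rises from 2.3% to between 2.7% and 6.8% over the amounts assumed here. Those figures rest on assumed hidden amounts, 150 evaluable subjects per arm and the planned pooled Z. They do not show that the trial's conclusion would be wrong.

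**What to change.** 1. **Outcome rule (Protocol 7.1.6 and 8.1, SAP 13.1).** State that re-opening, study-suture removal or re-suturing on or before the V4 photo, related to an incision complication or the study device, is analysed as not Grade A in FAS and PP.
   - State that this result is available primary-endpoint data. It is then part of the endpoint definition and not imputation, and it meets both the PP data requirement and the post-baseline evaluation that SAP 5.1 requires for the FAS.
   - State that the unplanned-procedure and major-deviation criteria do not remove these subjects.
   - Settle relatedness at the blind review before database lock, without arm labels, and list the cases by arm.
2. **Time limit (Protocol 8.8, SAP 5.2).** Limit the PP exclusion for unrelated re-opening to events before the V4 photo.

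**Cost.** The change is to wording. Complications, concomitant treatment and adverse events are already collected at V4, although a major protocol amendment needs ethics approval (Protocol 15). Relatedness will start from site reports, and the suturing investigator is unblinded (Protocol 7.1.3).

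Power may fall if the planned 98% did not already count such events as failures. The approximate power is Φ(0.05/√(2p(1 − p)/150) − 2.2414). It is 80.3% at p = 0.98. If success were lower by the same amount in all arms, it would be 70.3% at 0.975, 61.7% at 0.97 and 48.7% at 0.96. The sponsor should say what the 98% includes.

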7.1.3 Measures to Reduce and Avoid Bias

In the study, central randomization will be adopted to randomly assign eligible subjects to one of the three groups: investigational group 1, investigational group 2 or control group according to the same inclusion/exclusion criteria to reduce the impact caused by unknown confounding factors and avoid selection bias.

Study blinding is as follows:

- Subject: Subjects are informed prior to surgery that they will be randomized to any of the study groups with equal probability, and during the surgery, a blinding method will be adopted for them.
- Investigator responsible for incision suture: Considering the investigational groups and

[PROTOCOL VERISON AND DATE] V2.0/2019-09-30

control group use different shapes and usages of suture, it is impossible to blind investigators who are responsible for suturing.

- Central evaluator: Imaging data will be submitted to Imaging Center for assessment to assess the primary endpoint and the modified Hollander score among secondary endpoints. The Central Imaging evaluators will be blinded.
- Monitor: As the product information is specified on the detachable label supplied with the product and instrument counting and source document verification is - done with the study product inventory records and subject's medical record, the monitor will not be blinded.

In addition, this study will collect data about objective measures, study related information will be recorded in the source medical records as detailed as possible, the monitor will pay attention to verifying the data in the source medical records during the monitoring process, investigator training will be strengthened, and investigators will closely communicate with subjects to improve compliance of subjects. This will help to reduce the informational bias.

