## 5.1. FULL ANALYSIS SET (FAS)

FAS consists of all the enrolled subjects who were randomized and at least post-baseline effectiveness endpoint evaluation.

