#### **13.1.2. PRIMARY ANALYSIS OF PRIMARY EFFICACY VARIABLE(S)**

This is a non-inferiority trial with two treatment group comparisons, [REDACTED] versus control group, and [REDACTED] versus control group. The overall family-wise error rate is controlled at 0.025 level

using the Holm's multiple comparisons procedure. The expected proportion of successes is 0.98 for all the three groups.

For each of the two comparisons, the statistical hypotheses for testing the non-inferiority of the investigational group to control are presented as follows:

$H_0: P_T - P_C \leq -0.05$  tested against the alternative hypothesis

$H_a: P_T - P_C > -0.05$ .

$P_C$  is the proportion of successes (Grade A healing) in the control group and  $P_T$  is the proportion of successes in each of the investigational groups (1 and 2). The proportion of subjects with Grade A healing will be summarized for each treatment group and will be calculated as the number of subjects with Grade A healing divided by the total number of subjects randomized to that treatment who had the surgical wound closed using the randomized suture. Within-treatment group, two-sided 95% confidence intervals for the proportions of successes will be provided using the Clopper-Pearson method.

For the primary endpoint analysis, the Holm's step-down procedure will be used. For each of the two group comparisons, the p-value associated with the non-inferiority test will be calculated using the Normal approximation Z (pooled) statistic. If the smaller p-value is smaller than 0.0125, then the null hypothesis associated with this p-value will be rejected and it will be concluded that the associated Test product is non-inferior to Control; subsequently, the larger p-value will be compared to 0.025 in order to test the non-inferiority of the other Test product to Control. If the smaller p-value is larger than 0.0125, then neither of the null hypotheses can be rejected and it will be concluded that, for both investigational devices, the study failed to demonstrate non-inferiority to Control.

The primary endpoint will be analyzed using the Full Analysis Set (FAS) and Per-Protocol (PP) sets. The PP analysis will be considered the primary analysis, while the FAS analysis will be considered supportive.

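### The FAS is defined one way in the protocol and another in the SAP; the conflict reaches the PP set, which alone decides non-inferiority with no requirement that the FAS agree

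*Protocol*

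**What the plan says.** **Which set decides.** Protocol 8.1 and 8.8 and SAP 13.1.2 agree. Protocol 8.8 says that "while the primary analysis is based on the PP Set, FAS analysis will only be used as supplemental analysis". In the SAP's words: "The PP analysis will be considered the primary analysis, while the FAS analysis will be considered supportive". Protocol 8.5, which sets the criterion for success, names no analysis set.

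**FAS in Protocol 8.8.** "FAS consists of all the enrolled subjects who were randomized and for whom the randomized suture materials were used for incision closure".

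**FAS in SAP 5.1.** "FAS consists of all the enrolled subjects who were randomized and at least post-baseline effectiveness endpoint evaluation". The suture condition is gone. SAP 1 says the plan is based on protocol version 2.0, and no reason is given for the change.

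**Denominator.** SAP 13.1.2, like Protocol 8.1, divides by the "total number of subjects randomized to that treatment who had the surgical wound closed using the randomized suture". That is the protocol's FAS, not the SAP's.

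**PP.** In both documents PP is the FAS less subjects with a major deviation, without primary-endpoint data, or meeting a listed criterion. One criterion, for other unplanned surgery, has the exception "except the procedure that the investigator doesn't think it will affect the original incision's healing".

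**Blinding.** Randomisation comes before surgery, and Protocol 7.1.3 says "it is impossible to blind investigators who are responsible for suturing". The Day 5-7 grade is read centrally by blinded evaluators. SAP 5 has set membership agreed before unblinding, and Protocol 9 lists a blind review.

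**Missing data.** Protocol 8.7 and SAP 7.1: available data, no imputation.

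**The concern.** A supportive analysis is useful only if everyone knows in advance which subjects it contains. Here two programmers, one working from Protocol 8.8 and one from SAP 5.1, could build different FAS populations, and hence different PP populations, and each could cite a signed document.

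Both FAS versions also lose some randomised subjects after an operation by unblinded staff. The protocol version drops those not closed with the allocated suture; the SAP version drops those without a post-baseline evaluation. Neither is a full as-randomised check on PP. Since PP alone carries the claim, a PP pass with a FAS fail would still be declared non-inferior.

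At an expected 98% success rate each arm has about three failures (150 × 0.02), so the handling of one or two subjects can matter.

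**Working it through.** **1. The definitions side by side**

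| Subject | Protocol FAS | SAP FAS | Denominator (Protocol 8.1, SAP 13.1.2) | PP |
|---|---|---|---|---|
| A: closed with another suture, Day 5-7 image available | out | in | out | out under the protocol; in under the SAP unless graded a major deviation |
| B: closed with the allocated suture, no post-baseline evaluation | in | out | in | out in both |

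Subject A shows that the mismatch reaches the deciding set. Subject B shows a second conflict: the written denominator counts B as a non-success, while the available-data rule omits B.

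**2. The plan's sample size reproduces**

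Inputs (Protocol 8.2.1): 98% success in both groups, margin 0.05, one-sided 0.0125, 80% power.

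n = (2.2414 + 0.8416)² × 2 × 0.98 × 0.02 / 0.05² = 149.04, so 150 per arm. 150 / 0.90 = 166.7, so 167 per arm and 501 in total. Exact enumeration of the planned pooled Z test at 150 per arm gives 80.4% power. The sample size is not in dispute.

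**3. How many failures separate pass from fail**

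Z = (f_C/n_C − f_T/n_T + 0.05) / √[p(1 − p)(1/n_T + 1/n_C)], where f is the number of failures and p the pooled failure proportion. Control is set at 3/150, the planned 2%.

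| Test failures | Z | One-sided p | 0.0125 | 0.025 (Holm step 2) |
|---|---|---|---|---|
| 4/150 | 0.04333/0.01743 = 2.486 | 0.0065 | pass | pass |
| 5/150 | 0.03667/0.01860 = 1.971 | 0.024 | fail | pass |
| 6/150 | 0.03000/0.01970 = 1.523 | 0.064 | fail | fail |

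Excluding one failure from five leaves 4/149, p = 0.0068. Excluding two from six leaves 4/148, p = 0.0072. Excluding only one from six leaves 5/149, p = 0.0254, which just misses even the second step.

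**4. A range for selective exclusion (assumption, not a prediction)**

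Take true rates of 0.93 against 0.98, 150 per arm, and a fraction q of test failures alone excluded. The test rate within PP is then 0.93 / [0.93 + 0.07(1 − q)]. The exact rejection rate at nominal 0.0125 is 2.3% for q = 0, 3.2% for 5%, 4.3% for 10% and 7.8% for 20%. The 2.3% at q = 0 belongs to the test at these rates, not to selection.

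**5. The price of requiring both sets**

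Simulated per comparison at 0.0125, with PP at 150 per arm nested at random in the FAS and 98% success throughout:

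- FAS of 160 per arm (an assumed size): PP 80.4%, FAS 82.7%, both 78.5%.
- FAS of 167 per arm: FAS 84.9%, both 78.6%.

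This depends on how the FAS-only subjects fare. If the 10 extra subjects per arm succeed at 90% or 80%, FAS power alone is 74.2% or 64.5%. If a random 10% in every arm lack an image and count as non-successes, the expected rate is 0.98 × 0.90 = 0.882. Power at 167 per arm is then Φ(0.05/√(2 × 0.882 × 0.118/167) − 2.2414) = Φ(−0.825), about 20%, and about 792 per arm would be needed for 80%.

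**The case against.** PP as the primary set is a defensible choice for non-inferiority and is pre-specified consistently. Requiring both sets is partly a design preference. The two FAS definitions may also give much the same analysed subjects in practice: the denominator is common, nothing is imputed, and closure with the wrong suture would plausibly be a major deviation. All of that is fair, but plausibly is not a definition. Major deviations have a general description and no list.

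Three stronger readings are tempting, and the documents do not support them.

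- *A device abandoned during surgery disappears from the trial.* It does not. Protocol 7.2.3 records product code, quantity and tissue layer, and gives subjects with no study suture a withdraw visit for adverse events and complaints. Protocol 14.3 requires all complaints to be reported, SAP 9 tabulates deviations and set membership, and the protocol's Safety Set keeps everyone operated on. The subject leaves the efficacy proportion, not the record.
- *The surgeon can choose who counts.* The exception applies only where a further unplanned procedure took place. Exclusion is then the default, and the opinion can only keep a subject in. Re-openings related to an incision complication or the study device stay in PP. Protocol 7.2.3 requires closure by assigned group, so a swap is a deviation. That the investigator concerned is the unblinded operator is an inference; no blinded site role is assigned to the decision.
- *Requiring both sets is always cheap.* Step 5 shows that it is not.

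Agreement of the sets before unblinding and blinded central grading reduce the risk. They cannot blind an opinion already given at the site, and no time is set for recording it relative to Day 5-7.

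**Conclusion.** The point holds as a defect of definition and decision rule. Protocol 8.8, SAP 5.1 and SAP 13.1.2 cannot all be followed for every randomised subject. The conflict passes into PP, and nothing has to corroborate PP. The opinion-based exception is a secondary weakness of narrow scope.

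With 3/150 control failures the pass line is four test failures at 0.0125 and five at Holm's second step, so one or two exclusions could reverse a conclusion. Whether any would coincide with an excludable procedure is unknown. The figures in step 4 are a range under stated assumptions and do not show that the primary analysis is biased. The texts should be reconciled before database lock.

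**What to change.** 1. **One FAS.** In Protocol 8.8 and SAP 5.1: all randomised subjects who have the study surgery, analysed as randomised. Match the denominator in Protocol 8.1 and SAP 13.1.2 to it. Keep the Day 5-7 photograph for subjects closed with another suture; those with no study suture now have only the withdraw visit, which takes none. State one rule for missing images: available data, with a sensitivity analysis counting missing as non-success. Given the roughly 20% power in step 5, that analysis should not be part of the decision rule.
2. **Agreement.** State in Protocol 8.1, 8.5 and 8.8 and SAP 13.1.2 that a non-inferiority claim needs the PP and FAS results to agree.
3. **Masked decision.** Settle the unplanned-procedure exclusion at the existing pre-lock blind review, from a description of the additional procedure with suture details and the Day 5-7 grade masked. An unredacted operation note would reveal the arm.

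Cost: wording in both documents, some extra photographs, and a masked summary for the few subjects affected. Power per comparison falls from about 80.4% to 78.5% if FAS outcomes are essentially complete and success is 98% in all arms. It falls further if FAS-only subjects do worse or missing images count as failures, so item 1 must be settled before item 2.
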